9.3.1 Adverse Event Monitoring Rule

We will use a Bayesian rule to monitor for protocol-specific toxicities (list given below). We will assume a beta prior distribution with $\alpha = 0.52$ and $\beta = 2.08$. At least once per month, we will calculate the posterior probability (given the data) that the probability of protocol-specific toxicity exceeds the 20% threshold:

$$P(p_{\text{protocol-specified toxicities}} > 20\% \mid \text{Data}) = \int_{0.2}^1 \frac{\binom{n}{x} p^x (1-p)^{n-x} \frac{\Gamma(2.6)}{\Gamma(0.52)\Gamma(2.08)} p^{-0.48} (1-p)^{1.08}}{\int_0^1 \binom{n}{x} q^x (1-q)^{n-x} \frac{\Gamma(2.6)}{\Gamma(0.52)\Gamma(2.08)} q^{-0.48} (1-q)^{1.08} dq} dp$$

Here n is the number of protocol-specific toxicity-evaluable cycles and x is the number of such cycles on which a protocol-specific toxicity event is observed. If there is strong evidence (posterior probability of at least 70% with at least 2 observed toxicities) that there is a per course protocol-specific toxicity probability

of more than 20%, such information will be presented to the DSMC. Examples of situations in which this rule will indicate protocol-specific toxicities have been noted and are presented below:

| Number of failures | Number of patient-cycles |
|--------------------|--------------------------|
| 2 | 6 |
| 3 | 10 |
| 4 | 14 |
| 5 | 19 |
| 6 | 23 |
| 7 | 28 |
| 8 | 32 |
| 9 | 37 |
| 10 | 41 |
| 11 | 46 |
| 12 | 51 |
| 13 | 55 |
| 14 | 60 |

Protocol-specific toxicities of interest include CTCAE v5 Grade 3 or higher fatigue, ataxia, dizziness, ALT increase, AST increase, neutropenia, thrombocytopenia, nausea, and vomiting. For the purpose of this toxicity monitoring rule, patients with leukemia or solid tumors with bone marrow metastases are not evaluable for hematologic toxicities (neutropenia or thrombocytopenia) unless these persist for greater than 14 days after a bone marrow is negative for malignancy and the patient does not have evidence of recurrent disease.

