2.4 Pediatric Studies

2.4.1 Pediatric Phase 1 Studies

A pediatric phase 1/2 study of larotrectinib is ongoing. The phase 1 dose escalation component of this study has now completed enrollment and has been published.¹ This study used a modified rolling 6 design and enrolled children > 1 month to 21 years of age. Patients were treated with larotrectinib oral suspension or capsules. As of July 17, 2017, 24 patients with a median age of 4.5 years (0.1 – 18 years) have enrolled to 3 dose levels.¹ The most common diagnoses were infantile fibrosarcoma (n=8) and other soft tissue sarcoma (n=7). 17 patients had TRK fusions. The most common drug related AEs were generally mild increases in liver enzyme levels (AST and ALT in 10 [42%] of 24 patients each, 8 [33%] Grade 1), hematological toxicity (leukocyte count decreased and neutrophil count decreased in 5 [21%] of patients each) and vomiting in 5 (21%) of patients. Fatigue was observed in 3 (13%) of 24 patients; other neurological toxicities were rarely seen. Grade 3 treatment-related adverse events occurred in 4 (17%) of 24 patients: 1 each of ALT elevation, nausea, neutropenia, and ejection fraction decreased. No other cardiotoxicity was seen in the pediatric phase 1 study or on the adult phase 1 or 2 studies. There were no drug related Grade 4 or 5 adverse events. One DLT (Grade 3 ALT elevation in a patient with neuroblastoma without a TRK fusion) occurred at dose level 3 which led to larotrectinib discontinuation. No other patients discontinued larotrectinib for adverse events and a MTD was not identified. One patient had dose reduction for Grade 3 neutropenia in cycle 2. A recommended phase 2 dose of 100 mg/m²/dose BID with a maximum of 100 mg/dose was identified based on pharmacokinetics, response, and safety of this dose level. As of July 17, 2017, 22 patients were evaluable for response. Fourteen of the 15 (93%) evaluable patients with TRK fusions had PR (n=10) or CR (n=4). Responses were seen in patients with fusions involving each of the 3 NTRK genes and in patients with both infantile fibrosarcoma and other sarcomas. Responses were seen at all dose levels, but due to intrapatient dose escalation, only 3 patients with TRK fusion tumors were treated with larotrectinib at doses of less than 80% of the recommended phase 2 dose. Two patients with TRK fusion papillary thyroid

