5.1 Definition of Dose-Limiting Toxicity (DLT)

DLT will be defined as any of the following events that are possibly, probably or definitely attributable to protocol therapy.

Dose limiting hematological and non-hematological toxicities are defined differently.

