5.1.2 Hematological dose limiting toxicity

5.1.2.1 Hematological dose limiting toxicity is defined as:

- a) In patients with solid tumors evaluable for hematological toxicity (see [Section 3.2.6.1a](#)),
 - Grade 4 thrombocytopenia (platelet count $< 25,000/\mu\text{L}$) or Grade 4 neutropenia, not due to malignant infiltration.
 - Grade 3 thrombocytopenia that persists for ≥ 7 days
 - Grade 3 thrombocytopenia requiring a platelet transfusion on two separate days within a 7-day period
 - Grade 3 thrombocytopenia with clinically significant bleeding

- b) In patients with leukemia, DLT will be defined as failure to recover a peripheral ANC > 500/ μ L and platelets > 20,000/ μ L without transfusion by 42 days after the first treatment day, not due to malignant infiltration.

Note: Grade 3 or 4 febrile neutropenia will not be considered a dose-limiting toxicity.

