9.3 Methods of Analysis

Response criteria are described in [Section 10.2](#). A responder is defined as a patient who achieves a best response (as defined in [Section 10.3.4](#)) of PR or CR on the study. Response rates will be calculated as the percent of evaluable patients who are responders, and confidence intervals will be constructed accounting for the two-stage design.

Toxicity tables will be constructed to summarize the observed incidence by type of toxicity and grade. A patient will be counted only once for a given toxicity for the worst grade of that toxicity reported for that patient. Toxicity information recorded will include the type, severity, time of onset, time of resolution, and the attribution(s) to the study regimen.

Time-to-event analyses (time to progression, progression-free survival, overall survival, and duration of response) will be computed one year after the last enrollment in a stratum. Duration of response will be defined among patients with a confirmed best response of either PR and CR, and will be defined as the time from the first observation of either PR or CR until either the first observation of PD (event) or last known observation of the patient (censored observation).

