11.4.2 Persistent AEs

A persistent AE is one that extends continuously, without resolution between treatment cycles/courses.

ROUTINE reporting: The AE must be reported only once unless the grade becomes more severe in a subsequent course. If the grade becomes more severe the AE must be reported again with the new grade.

EXPEDITED reporting: The AE must be reported only once unless the grade becomes more severe in the same or a subsequent course.

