11.11 Routine Reporting of Adverse Events

Note: The guidelines below are for routine reporting of study specific adverse events on the COG case report forms and do not affect the requirements for CTEP-AERS reporting.

Routine reporting is accomplished via the Adverse Event (AE) Case Report Form (CRF) within the study database. For this study, routine reporting will include all CTEP-AERS reportable events and Grade 3 and higher Adverse Events.

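### Does the toxicity monitoring rule in Section 9.3.1 leave open whether its minimum of 2 counts cycles or separate events?

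*Combined protocol and SAP*

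**What the plan says.** Section 9.3.1 puts a beta prior with parameters 0.52 and 2.08 on the probability of a listed toxicity. At least monthly it computes the posterior probability that this exceeds 20%. The denominator n is the number of toxicity-evaluable cycles, and "x is the number of such cycles on which a protocol-specific toxicity event is observed". A report goes to the DSMC at a "posterior probability of at least 70% with at least 2 observed toxicities", and the target is described as a per-course probability. The example table pairs failures with patient-cycles, from 2 in 6 to 14 in 60. Grade 3 or higher neutropenia is on the list.

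Other sections bear on how a continuing event might be counted:

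- Section 5.1.2, for solid tumors, makes thrombocytopenia of stated kinds a DLT, "or Grade 4 neutropenia, not due to malignant infiltration". Grade 3 neutropenia alone is not one.
- Section 5.1 has an attribution condition ("DLT will be defined as any of the following events that are possibly, probably or definitely attributable to protocol therapy"). Section 9.3.1 states none.
- Section 11.4.2, on routine reporting of persistent events: "The AE must be reported only once unless the grade becomes more severe in a subsequent course".
- Section 11.11: "routine reporting will include all CTEP-AERS reportable events and Grade 3 and higher Adverse Events".
- Section 9.3: "Toxicity information recorded will include the type, severity, time of onset, time of resolution".

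**The concern.** One rule uses three nouns (cycles, toxicities, failures) and never equates them. It also does not say in so many words whether an event that continues into a second cycle adds to x again.

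For most listed toxicities this hardly matters, since the hold and 21-day rules in Section 5 make a multi-cycle event unlikely. Grade 3 neutropenia is different. It is monitored but does not by itself hold treatment, and after Cycle 1 blood counts are scheduled only before each cycle (Section 4.3.2). Its recorded interval can therefore straddle cycles. A count taken from form entries would show one record, while a count of cycles would show two or more.

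Two statisticians could then disagree at the same monthly look on the same data. What is at stake is whether the DSMC is sent a report.

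**Working it through.** **Inputs (Section 9.3.1).** Prior Beta(0.52, 2.08); threshold 0.20; report at posterior ≥ 0.70 together with the minimum of 2.

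**Formula.** P(p > 0.20 | x, n) = 1 − F(0.20; 0.52 + x, 2.08 + n − x), where F is the beta distribution function.

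**Reproducing the table.** For each x from 2 to 14, take the largest n with posterior ≥ 0.70. All 13 rows match. The first is 2 of 6 (0.7001; 0.6318 at n = 7) and the last is 14 of 60 (0.7135; 0.6908 at n = 61). The table is the rule with x in cycles.

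**What the minimum does.** With x = 1 the posterior is 0.7995 at n = 1 and 0.6936 at n = 2. On a cycle count the minimum therefore removes one case only, 1 of 1. That is why the table starts at 2.

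**One neutropenia lasting two cycles:**

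| Reading | Count at n = 6 | Posterior | Report? |
|---|---|---|---|
| x and minimum both in cycles | 2 of 6 | 0.700 | yes |
| x in cycles, minimum in separate events | 2 of 6, one event | 0.700 | no |
| onset cycle only | 1 of 6 | 0.358 | no |

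With x = 2 a report is due for n = 2 to 6 (0.944 falling to 0.700) and not at n = 7 (0.632). Here n is the trial's cumulative number of evaluable cycles, not one child's, so the example belongs to the first few weeks of data.

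**Later looks.** Six children with two cycles each, two of them neutropenic throughout, give 4 of 12 (0.816) if every affected cycle counts and 2 of 12 (0.340) if only onset counts. The minimum plays no part here; the question is only how a continuing event is scored. As data accumulate, one lingering event matters less. If 21 children had 12 cycles each (the 12 is assumed), n = 21 × 12 = 252. The boundary is then 54 affected cycles (0.702; 53 gives 0.646), and one event lasting two or three cycles decides nothing unless x is already next to it.

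**A minimum in separate events.** One event over two cycles is 2 of 6, and one event over three cycles can be 3 of 10 (0.715). Both are printed as situations that trigger, yet neither would. Conversely, two different listed toxicities in the first evaluable cycle (ALT and AST are listed separately) give x = 1, n = 1, posterior 0.7995, with two events. That would be reported although the table has no such row.

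**Illustrative size.** A simulation used 21 children, 8 per year, 12 cycles each, Grade 3 neutropenia for three cycles from Cycle 1 and no other events. The number of cycles, the onset and the duration are assumptions. Chance of any report:

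| Share of children affected | Onset only | Every cycle, minimum in cycles |
|---|---|---|
| 1/24 (4%) | 0.4% | 7% |
| 10% | 2% | 18% |
| 5/24 (21%) | 7% | 37% |

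With onset at random in Cycles 1 to 3, the 4% row becomes 0.1% and 4%. Only the 4% row matches a documented Grade 3 rate: Section 2.4.1 gives one drug-related Grade 3 neutropenia in 24 children. The 21% end comes from "leukocyte count decreased and neutrophil count decreased in 5 [21%] of patients each", which is not restricted to Grade 3.

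**The case for a change.** The best case for amending is that a prespecified monthly safety rule should be reproducible from its text, and one sentence would make it so. The wording is loose. Whether a continuing event counts in every cycle or only at onset is not confined to the first six cycles, as 4 of 12 against 2 of 12 shows. Grade 3 neutropenia can realistically continue on treatment. Section 9.3.1 is also silent on events judged unrelated.

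The looseness stands as a matter of drafting. It does not leave the analyst without an answer:

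- A cycle on which a listed event is present is a cycle on which it is observed. That is the plain reading of x, and it suits a per-course target.
- Sections 11.4.2 and 11.11 govern what sites submit, not how the statistician counts. Onset and resolution times are recorded, so affected cycles can be derived however many form entries exist.
- With no attribution condition in Section 9.3.1, listed events count as they occur. Section 9.5 mentions toxicity at least possibly related to the regimen, but there it settles which patients are evaluable. Counting all listed events errs toward reporting, which is the safer direction for an alarm that only informs the DSMC.

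**Conclusion.** No change is needed. Read as its own definition and table direct, the rule counts affected evaluable cycles throughout, requires at least two of them, and is arithmetically correct in all 13 rows. The wording of the minimum is a drafting slip that its context resolves.

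Where the readings differ, the difference is real but small in consequence. For a single two-cycle event it is confined to n of 6 or fewer. Section 2.7.1 says accrual is complete, so that case can no longer arise. For continuing events generally, the literal reading yields more reports than onset counting: about 7% against 0.4% at the documented Grade 3 rate, under the assumed durations above. Each is a report for discussion, with no automatic stop, and Section 12.2 separately requires unexpected frequencies of serious events to go to the DSMC. A minimum stated in separate events would conflict with the printed table.

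The conclusion rests on x meaning what Section 9.3.1 says it means. The simulated percentages are illustration only and do not carry it.

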2.3 Adult Studies

2.3.1 Adult Phase 1 Studies

In a phase 1 trial, there was no biomarker required for eligibility, but 8 of 59 enrolled patients had TRK fusions. This study identified a recommended phase 2 dose in adults of 100 mg BID based on exposure, response, and toxicity, but no MTD was reached in adults treated at doses up to 200 mg BID. Larotrectinib was well tolerated in this study, with the most common adverse events regardless of attribution being fatigue, dizziness, dyspnea, and anemia. Few Grade 3/4 adverse events were observed, with fatigue, anemia, dyspnea, increased AST, decreased appetite, lymphocyte count decreased, and pneumonia being the only recurrent Grade 3 events, each occurring in less than 10% of patients. Among the 8 patients with TRK fusions, 7 were evaluable for response as of the last data cut off (November 10, 2016). Six of the 7 evaluable patients achieved confirmed partial responses and all patients remained in response at a median of >15 months of larotrectinib therapy. The seventh patient with a TRK fusion did not have measurable disease at enrollment but remained on study with stable disease for >12 months. No responses were seen in patients without TRK fusions.

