4.2.2 Required Observations in Cycle 1, Cohorts A & B

All baseline studies must be performed prior to starting protocol therapy unless otherwise indicated below.

- a. Hx/Wt /Ht/BSA. Within 7 days prior to Cycle 1.
- b. Performance status. Prior to Cycle 1.
- c. Physical exam (including VS and neurologic examination). Prior to Cycle 1.
- d. CBC/diff/platelets: Prior to Cycle 1 and every week during Cycle 1. If patients have Grade 4 neutropenia then CBCs should be checked every 3 to 4 days until recovery to Grade 3 or until meeting the criteria for dose limiting toxicity.
- e. Electrolytes including Ca⁺⁺. Prior to Cycle 1.
- f. Creatinine, ALT, bilirubin. Prior to Cycle 1.
- g. Albumin. Prior to Cycle 1.
- h. Disease evaluation. Prior to Cycle 1.
- i. Pregnancy test. Prior to Cycle 1. Female patients of childbearing potential require a negative pregnancy test prior to starting treatment; sexually active patients must use an acceptable method of birth control.
- j. Bone marrow evaluation. Prior to Cycle 1. Bone marrow aspirate and/or biopsy should only be performed on patients with solid tumors with known bone marrow metastasis on the basis of history, symptoms, laboratory evaluation or other clinical data.
- k. Circulating tumor DNA. Prior to Cycle 1 and on Day 15 of Cycle 1. See [Section 7.3.2](#) for details.
- l. Tumor tissue submission. Prior to Cycle 1. If tissue blocks or slides are unavailable, the study chair must be notified prior to study enrollment. See [Section 7.3.1](#) for details.
- m. Patient diary. Uploaded into RAVE at the end of Cycle 1. See [Appendix VII-A](#) and [Appendix VII-B](#) for details.
- n. Neurocognitive assessments. Within 4 weeks after enrollment. See [Section 3.1.7](#) and [Appendix XI](#) for details.

This listing only includes evaluations necessary to answer the primary and secondary aims. OBTAIN OTHER STUDIES AS REQUIRED FOR GOOD CLINICAL CARE.

Comments

(Include any held doses, or dose modifications)

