4.3.2 Required Observations for Cycles 2+, Cohorts A & B

- a. Hx/Wt /Ht/BSA. Within 7 days prior to subsequent cycles and at the end of study treatment.
- b. Performance status. Prior to subsequent cycles.
- c. Physical exam (including VS and neurologic examination). Prior to subsequent cycles and at the end of study treatment.
- d. CBC/diff/platelets: Prior to subsequent cycles. If patients have Grade 4 neutropenia then CBCs should be checked every 3 to 4 days until recovery to Grade 3 or until meeting the criteria for dose limiting toxicity.
- e. Electrolytes including Ca⁺⁺. Prior to subsequent cycles.
- f. Creatinine, ALT, bilirubin. Prior to subsequent cycles.
- g. Disease evaluation. After cycles 2, 4, 6, 9, 12, 16, 20, and 24. If the institutional investigator determines that the patient has progressed based on clinical or laboratory evidence, he/she may opt not to confirm this finding radiographically. Please refer to [Section 10.4](#) for Confirmation of objective response by RECIST 1.1.
- h. Bone marrow evaluation. With Disease evaluation. Bone marrow aspirate and/or biopsy should only be performed on patients with solid tumors with bone marrow involvement at baseline. If the institutional investigator has determined the patient has progressed based on clinical or laboratory evidence, he/she may opt not to confirm this finding on marrow pathology.
- i. Circulating tumor DNA. On Day 1 of Cycle 2, at the end of cycle 6 (Day 1 of Cycle 7 or prior to local control), and at the time of progression. See [Section 7.3.2](#) for details.
- j. Tumor tissue submission. Submission of tumor tissue from any surgical resection or bone marrow evaluation for patients with involvement by tumor while on study is required. For patients who undergo resection of their tumor while on study, operative reports and hospital discharge summaries must be uploaded into RAVE following surgical resection. Submission of tumor tissue from any biopsy after progression is optional. See [Section 7.3.1](#) for details.
- k. Patient diary. Uploaded into RAVE at the end of each cycle. See [Appendix VII-A](#) and [Appendix VII-B](#) for details.
- l. Pregnancy test. Prior to subsequent cycles. Sexually active patients must use an acceptable method of birth control.

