5.1.1 Non-Hematological Dose-Limiting Toxicity

5.1.1.1 Any Grade 3 or greater non-hematological toxicity with the specific exception of:

- Grade 3 fatigue, nausea, or vomiting of < 3 days duration
- Grade 3 ALT/AST/GGT that return to levels that meet initial eligibility criteria within 7 days of study drug interruption and that do not recur upon re-challenge with study drug. Note: For the purposes of this trial the ULN for ALT is defined as 45 U/L and the ULN for AST as 50 U/L. See [Appendix XII](#) for values that represent thresholds between CTCAE grades.
- Grade 3 or 4 total bilirubin elevation in infants who enrolled with physiologic jaundice and in patients with leukemia. For such patients, only the conjugated (direct) bilirubin will be considered a dose limiting toxicity.
- Grade 3 or 4 fever
- Grade 3 infection < 5 days duration
- Grade 3 weight gain
- Grade 3 hypophosphatemia, hypokalemia, hypocalcemia and/or hypomagnesemia responsive to oral supplementation

5.1.1.2 Any Grade 2 non-hematological toxicity that persists for ≥ 7 days and is considered sufficiently medically significant or sufficiently intolerable by patients that it requires treatment interruption will be considered a dose limiting toxicity.

- Grade 2 allergic reactions that necessitate discontinuation of study drug will not be considered a dose-limiting toxicity.

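### Grade 3+ AST increase counts toward the toxicity alert, but no required laboratory panel measures AST, so isolated AST events may be missed.

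*Combined protocol and SAP*

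**What the plan says.** Section 9.3.1 lists the Grade 3+ events that count toward notifying the DSMC: fatigue, then "ataxia, dizziness, ALT increase, AST increase, neutropenia, thrombocytopenia, nausea, and vomiting". The unit is the cycle: "x is the number of such cycles on which a protocol-specific toxicity event is observed". Appendix XII sets an AST upper limit of normal of 50 U/L and a Grade 3 band of 251 to 1000 U/L.

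The chemistry required in Cohorts A and B is "Creatinine, ALT, bilirubin. Prior to Cycle 1" (section 4.2.2) and "Creatinine, ALT, bilirubin. Prior to subsequent cycles" (section 4.3.2). Sections 4.4.2 and 4.5.2 repeat this for Cohort C, and table 7.1 has one matching row. The pre-treatment recheck in section 3.2 names only bilirubin and ALT for the liver. AST and GGT are on none of these lists.

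The DLT definition in section 5.1.1.1 exempts "Grade 3 ALT/AST/GGT that return to levels that meet initial eligibility criteria within 7 days of study drug interruption", provided they do not recur on re-challenge. For infants enrolled with physiologic jaundice and for patients with leukemia, "only the conjugated (direct) bilirubin will be considered a dose limiting toxicity".

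**The concern.** A monitoring rule can count only what is measured. Evaluability for toxicity in section 9.5 depends on dose received or on a related toxicity, not on which tests were done. A cycle with no AST result can thus add to n and nothing to x. Any resulting error runs one way: a missed AST event can lower x but never raise it.

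The protocol's own standard points to the same gap. Each list of required observations says that it holds the evaluations needed for the primary and secondary aims, and describing toxicity is secondary aim 1.2.3. Section 2.2.2 names the liver as the most sensitive organ in both toxicology species. In section 2.3.1 AST is the liver test among the recurrent Grade 3 events in adults ("fatigue, anemia, dyspnea, increased AST, decreased appetite", with others). At stake are the input to the safety alert and the AST row of the toxicity table, both of which would depend on which sites happen to run a wider panel.

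**Working it through.** **1. Event terms against required tests.**

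| Analyte | In alert rule (9.3.1) | In DLT wording (5.1.1.1) | Required at baseline | Required on treatment |
|---|---|---|---|---|
| ALT | yes | yes | yes | yes |
| AST | yes | yes | no | no |
| GGT | no | yes | no | no |
| Conjugated bilirubin | no | yes, two groups only | yes: leukemia, and infants admitted despite raised total bilirubin from jaundice (3.2.6.3) | fraction not specified |

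AST is the only liver analyte that is in the alert rule and in no required panel.

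**2. The plan's own alert table.** Section 9.3.1 states: "We will assume a beta prior distribution with" α = 0.52 and β = 2.08, so the prior mean is 0.52/2.60 = 0.20. An alert needs x ≥ 2 and P(p > 0.20 | x, n) ≥ 0.70, where p | x, n ~ Beta(0.52 + x, 2.08 + n − x). Taking for each x the largest n that still alerts reproduces all 13 rows. For example, 2/6 gives 0.7001 and 2/7 gives 0.6318; 14/60 gives 0.7135 and 14/61 gives 0.6908. The arithmetic of the rule is sound, so the issue is ascertainment of events.

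**3. One missed event at the boundary.**

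- 2/6: Beta(2.52, 6.08), posterior 0.700, alert. With one event missed, 1/6: Beta(1.52, 7.08), posterior 0.358, no alert.
- 3/10: posterior 0.715, alert. With one event missed, 2/10: posterior 0.443, no alert.

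The 2/6 case sits on the threshold, so losing any event there reverses it. These figures show sensitivity to one event. They do not estimate an effect.

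**4. Range over an unknown share.** Each cycle counts once, so a missed AST lowers x only if no other listed Grade 3+ event was recorded in that cycle. Let m be the share of event cycles that are isolated, undetected Grade 3+ AST. The observed rate is then p(1 − m); for example, 0.25 × 0.90 = 0.225. The documents give no value for m. Assuming independent cycles and the rule applied after each of 60 cycles (the last n in the plan's table), the probability of an alert is:

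| True rate per cycle | m = 0 | 5% | 10% | 20% | 30% |
|---|---|---|---|---|---|
| 25% | 0.865 | 0.821 | 0.770 | 0.648 | 0.510 |
| 30% | 0.966 | 0.946 | 0.918 | 0.831 | 0.700 |

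**5. The DLT passages.** The exception in 5.1.1.1 tests AST and GGT against the initial eligibility criteria, but 3.2.6.3 sets limits only for ALT, bilirubin and albumin. Section 5.3.1 also allows recovery to baseline, yet no baseline AST or GGT is required. The exception uses a 7-day window, but no liver recheck is scheduled during a hold: 5.2.1 sets an interval for blood counts and 5.3 sets none.

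**The case against.** The strongest reply is that m may be close to zero. ALT is both listed and measured. In the pediatric phase 1 study (section 2.4.1) AST and ALT each rose in 10 of 24 patients, with 8 of the 10 at Grade 1. The four related Grade 3 events there were one each of ALT elevation, nausea, neutropenia and decreased ejection fraction, with none for AST. In the adult study each recurrent Grade 3 event occurred in fewer than 10% of patients. Sites may run AST as clinical care, section 11.11 requires any Grade 3+ event found to be reported, and under section 12.2 the DSMC reviews toxicity beyond this rule. Section 6.1 is blacked out, so any monitoring text there cannot be assessed. All of this stands, and it limits the claim to events that may be missed. It does not supply the measurement: reporting captures only what somebody tested.

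A reader might infer more than the documents support:

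- That hepatic alerts are in fact under-counted. No figure for isolated, undetected AST is given. The 42% who had an AST rise (10/24) is no guide to Grade 3+ events.
- That conjugated bilirubin is never required. Section 3.2.6.3 requires it at baseline in leukemia and in infants admitted despite raised total bilirubin from jaundice. The gap is only that the on-treatment panel does not specify the fraction.
- That the GGT and bilirubin gaps weaken the alert. Neither is in the 9.3.1 list.
- That the gaps in the DLT exception lower the DLT count. The clause removes events from DLT status. If its test cannot be met, a detected Grade 3 event remains a DLT.

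**Conclusion.** The mismatch is established from the text: Grade 3+ AST increase is a named alert event with its own grading limits, and no required panel in any cohort measures AST. Isolated Grade 3+ AST events may be missed, and any resulting bias in x and in the AST toxicity table is downward. Its size cannot be estimated. Under the assumptions in the working, at a true rate of 25% the chance of an alert within 60 cycles is unchanged at 0.865 if m = 0, and falls to 0.770 if m = 10% and to 0.648 if m = 20%.

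The DLT wording is a separate inconsistency between sections 3.2.6.3, 5.1.1.1, 5.3 and the schedule. It bears on holding and reducing drug. Section 9 plans no analysis of DLT rates, so it touches neither the alert nor a planned endpoint.

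**What to change.** Add AST to the creatinine, ALT and bilirubin panel in sections 4.2.2, 4.3.2, 4.4.2, 4.5.2 and table 7.1. The alert table itself needs no change.

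Section 2.7.1 says that accrual is complete, so an amendment helps only patients still on treatment and cannot recover AST results never obtained. For cycles already completed, report how many evaluable cycles had AST measured, and do not count the others as free of AST events. In practice, use cycles or patients with an AST result as the denominator of the AST row, and show x/n and the posterior both for all evaluable cycles and for those with an AST result. The second version may err upward where AST was ordered on suspicion, and the report should say so.

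Separately, the sponsor should reconcile the references in 5.1.1.1 to AST, GGT and conjugated bilirubin, the limits in 3.2.6.3, the on-treatment schedule and the 7-day window. The choice of levels, analytes and recheck timing is the sponsor's.

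The cost is amendment wording and a query to sites for AST results already held. I assume that AST can be run on the blood already drawn for ALT; the documents do not say so.
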